Intitulé de l'étude	Covid-19 Pandemic Triage Score (STC-19)
Sponsor	Groupe Hospitalier de la Rochelle Ré Aunis
NCT number	NCT04371471
PI	[name] [name]
Organisation responsible for the analysis (if different)	NUMAHEALTH INTERNATIONAL
Responsible for analysis (if different)	[name]
Methodology of reference (in France)	 MR-004  MR-005  MR-006
Data sources	 Medical records  Survey / Cohort / Register including data from the national health data system  Medicalization Program of Information Systems  Other source of Data
Background	The aim of the health system is to prevent the occurrence of COVID-19 pneumonia and its progression to acute respiratory distress syndrome (ARDS), which has a high mortality rate. There is currently no known method of predicting which cases will progress to ARDS. In ARDS, inflammation of the lungs renders mechanical ventilation ineffective due to the occurrence of alveolar edema.
Context of the study	Inflammation is the common denominator in the mechanisms resulting in death, be it acute respiratory distress syndrome (ARDS), sepsis or end-organ failure ¹ . Many studies have already associated inflammatory burden with mortality. It remains unclear which markers of inflammation are most strongly correlated and at what point of hospitalization. C-Reactive Protein (CRP) is a well-studied marker of acute inflammatory reactant in patients with COVID-19 ² . However, there are other indicators or actors in acute inflammation. For example, the neutrophil-to-lymphocyte ratio (NLR) ³⁻⁹ is associated with mortality on admission for patients with COVID-19 ⁴ . It is has been referred to as the genito-thyroid index(GTi) ¹⁰ . Another marker is serum cortisol. High serum cortisol at admission to the hospital was associated with higher mortality in one study ¹¹ , but the opposite has also been observed ¹² . Tissue levels have not consistently been associated with severity of illness ^{13,14} . Our group ([name], [name]) has demonstrated that the effective tissue-level activity of cortisol can be modeled using a complete blood count with differential

	
(CBC)¹⁵ in chronic heart failure and acute myocardial infarction (AMI)^{16,17} and that the model of admission cortisol activity was superior to serum cortisol in predicting mortality in AMI⁸.
 
All current solutions focus on targeted treatment of the virus in an attempt to neutralize its epidemic spread and correct its downstream effects on the infected patient's body. We propose a radically different orientation which consists of starting from the patient, rather than the viral aggressor, by analyzing the state of his or her current adaptive response to the viral aggression.

Objective(s)	
To evaluate changes in biomarkers associated with inflammation to determine :
 
 1) at what point in the first 5 days of hospitalization would factors associated with deterioration or death be present, 2) which biomarker or indexes related to inflammation best predicted this deterioration or death.
Design	Single center retrospective study
Study population	Patient with clinical signs of CoV-2-SARS infection and signs of severity (polypnea, saturation < 90% room air, dyspnea, systolic blood pressure < 90 mmHg, altered consciousness, somnolence, confusion) and/or co-morbidities (> 70 years of age, Respiratory pathology at risk of decompensation, Chronic renal failure on dialysis, Heart failure or IV, Cirrhosis ≥ B, Cardiovascular history, Diabetes with poor balance or co-morbidities, Immunosuppression, Dementia)
Ethics committee	Study approved by the local ethics committee on 7 May 2020
Method	From medical records patients' information, coded, anonymized data will be entered regarding age, sex, blood pressure, oxygen saturation, survival status, CRP, and a CBC with differential from the time of admission, days 2-3 and 3-5.
Statistical analysis plan	
Demographic and biologic data will be used to describe the study population and to calculate the STC-19 score. Patient status (deceased or alive within 28 days after hospital admission) will be recorded. Categorical data will be collected for inclusion/exclusion criteria, gender, and patient living status. Continuous data will be collected for the complete blood count test.
 
Means and standard deviations, numbers, percentages and confidence intervals will be used to describe quantitative and qualitative variables, respectively.
 
Association between factors (age, creatinine, CRP, cortisol, genito-thyroid index) and death will be studied.
 
The STC-19 score will be calculated by the NumaHealth International statistician according to their proprietary calculation.

Justification of the public interest character of the study	If this score is validated, it will provide care recommendations determined by the number of factors in the severe or moderately severe pathophysiology zones. It will allow an immediate reduction in access to hospital resources and a reduction in the over-servicing of emergency and intensive care units when the patient's clinical condition permits without secondary risk to the patient.
Timetable for the study and provisional schedule for communicating the results	Data collection of patients hospitalized between March and May 2020 : from June to July 2020 Analysis and communication of results : From August to October 2020

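### The plan names a best predictor, and looks for when predictors appear, by comparing several markers in one cohort, with no allowance for that selection

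*Combined protocol and SAP*

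**What the plan says.** The Objective(s) row sets two aims. The first is to find "at what point in the first 5 days of hospitalization would factors associated with deterioration or death be present". The second is to find "which biomarker or indexes related to inflammation best predicted this deterioration or death".

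The Method row provides repeated sampling: "CRP, and a CBC with differential from the time of admission, days 2-3 and 3-5". Creatinine and serum cortisol are not in that data list.

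The Statistical analysis plan row answers the objectives with one sentence: "Association between factors (age, creatinine, CRP, cortisol, genito-thyroid index) and death will be studied". It adds a composite index: "The STC-19 score will be calculated by the NumaHealth International statistician according to their proprietary calculation". The outcome is a single binary one: "Patient status (deceased or alive within 28 days after hospital admission) will be recorded". The only methods named are descriptive: "Means and standard deviations, numbers, percentages and confidence intervals will be used to describe quantitative and qualitative variables, respectively".

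The Design row gives one centre and retrospective data. The Timetable row gives a calendar window ("Data collection of patients hospitalized between March and May 2020") but no number of patients or deaths. The public-interest row makes care recommendations depend on the score being validated, yet no validation step is described. No performance measure, ranking rule, resampling or hold-out sample appears anywhere.

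**The concern.** Objective 2 is a selection: markers are compared and one is named best. Objective 1 adds a second dimension, because deciding when predictive factors appear means looking at the same markers in several windows. When the leading estimate is both chosen and reported from the same patients, part of its lead is chance. Its apparent discrimination is then too high on average, and the order of the markers can change from one cohort to the next.

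The result is meant to feed a triage score and, through it, decisions on hospital resources. Overstated discrimination, or a ranking presented as firmer than it is, would carry straight into that use.

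**Working it through.** **No planned figure to reproduce.** The documents give no sample size, number of deaths, significance level or power.

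**Step 1: count the candidates.** The count depends on the reading. The last column is the chance of at least one association at an assumed 5% level if nothing predicts and the tests are independent, 1 − 0.95^k.

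| Reading | k | 1 − 0.95^k |
|---|---|---|
| The five listed factors, once each | 5 | 22.6% |
| CRP and genito-thyroid index × 3 windows | 2 × 3 = 6 | 26.5% |
| CRP, cortisol, genito-thyroid index × 3 | 3 × 3 = 9 | 37.0% |
| The same plus age | 9 + 1 = 10 | 40.1% |
| Four laboratory factors × 3, plus age | 4 × 3 + 1 = 13 | 48.7% |
| The same plus the STC-19 score × 3 | 13 + 3 = 16 | 56.0% |

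The markers are correlated, so these are upper figures. Simulated with correlation, 13 candidates gave 29 to 43% and 10 gave 29 to 31%.

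**Step 2: overstatement of the winner when all candidates are equal.** Assumptions: normal markers; 20% mortality; 13 candidates, each with true AUC 0.70; correlation 0.5 to 0.8 within a marker over time and 0.2 to 0.5 between markers; 2,000 runs per setting. The highest AUC is selected and its mean excess over 0.70 recorded.

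| Patients | Deaths | Mean excess |
|---|---|---|
| 50 | 10 | +0.103 to +0.129 |
| 100 | 20 | +0.072 to +0.091 |
| 200 | 40 | +0.050 to +0.065 |
| 400 | 80 | +0.035 to +0.046 |

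The exact count matters little. With 20 deaths and correlations 0.7 and 0.3, 13 candidates gave +0.083 and 10 gave +0.075. For the lowest reading, five candidates, a hand approximation is enough. The Hanley–McNeil standard error of an AUC of 0.70 with 20 deaths and 80 survivors is √{[0.21 + 19(0.5385 − 0.49) + 79(0.5765 − 0.49)] / 1600} ≈ 0.0705. The expected maximum of five independent standard normal values is 1.163. With correlation 0.3 the excess is about 0.0705 × 1.163 × √0.7 ≈ 0.069; direct simulation of this case gives 0.064.

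**Step 3: stability of the ranking.** Same correlations, 13 candidates.

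*Near tie* (one marker truly 0.72, 0.75 and 0.72 across the windows; all others 0.70):

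| Deaths | Right marker first | Right marker and window first |
|---|---|---|
| 10 | 34–38% | 17–22% |
| 20 | 41–47% | 24–31% |
| 40 | 53–60% | 36–47% |
| 80 | 67–77% | 52–68% |

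*Clear leader* (0.78, 0.80 and 0.78; all others 0.60; correlations 0.7 and 0.3): the right marker comes first in 92% of runs with 10 deaths and 98 to 100% with 20 or more. The excess falls from +0.060 with 10 deaths to +0.011 with 80. The right marker-and-window pair is still missed in 58% of runs with 10 deaths and 29% with 80, although the leader's windows differ by only 0.02 in true AUC, so such a miss costs little discrimination.

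**Step 4: what a correction recovers.** One setting was tested: 100 patients, 20 deaths, 13 candidates at 0.70, correlations 0.7 and 0.3, 200 data sets with 100 resamples each, the whole selection repeated in every resample. The winner's AUC fell from 0.786 to 0.732. The bias fell from 0.086 to 0.032, so (0.086 − 0.032)/0.086 ≈ 63%, or about 60%, was removed.

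**The case against.** The strongest reply is that the plan does not state the problem in this form. Its analysis sentence lists five associations with death and does not say that they are repeated by window. Creatinine and serum cortisol are not among the data collected by window, and age and creatinine are not presented as inflammation markers. This stands: any single count is a reader's construction, and a reader who settles on 13 candidates and a false-positive chance near one half goes beyond the text. The point survives because the excess is material even with five candidates.

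Three other inferences are tempting and are not supported.

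- *Objective 1 seeks the best window.* It asks when factors are present, which is a timing question. It still requires several windows to be examined, so selection enters, but not necessarily as a search for the highest AUC. The stem of the objectives also speaks of changes in biomarkers, which the simulations do not model.
- *The winner would probably fail to reproduce.* This depends on the true differences. In a near tie with few deaths the right marker is usually missed; with a clear leader it is almost always found.
- *Only the admission sample is legitimate for triage.* No section says so, and making admission primary would re-rank the sponsor's own objective about the first five days.

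It can also be said that this is a modest exploratory study. The plan does not call itself exploratory, and naming a best predictor is a comparative claim. The modest scale does argue against adding multiplicity-adjusted tests and simultaneous-interval rules on top of a resampling correction.

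**Conclusion.** The concern holds in a limited form. Following the plan as written would name a leading marker, and describe when it becomes informative, from a comparison in one cohort with no allowance for the comparison itself. The leader's apparent performance is biased upwards in expectation, and the ranking is unreliable if the markers perform alike.

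The size is conditional. It rests on an assumed 20% mortality, assumed numbers of deaths, AUC as the measure (the plan names none) and equal true AUCs of 0.70, a case that favours a large bias. On those terms, with 13 candidates, the overstatement is about 0.10 to 0.13 with 10 deaths and 0.04 to 0.05 with 80. With a clear leader it is 0.06 or less. The documents do not show which case applies.

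**What to change.** Before analysis, fix the candidate list, including whether cortisol means a serum assay or the index modelled from the blood count and whether the STC-19 score competes, and fix one performance measure, for example AUC for 28-day death. Then:

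- report every marker in every window with its confidence interval and the numbers of patients and deaths contributing;
- compare markers within a window on the patients sampled in that window. Restricting all windows to patients with a complete series would drop those who died or left before the last sample, and so remove early deaths from the admission analysis;
- repeat the whole selection inside at least 1,000 bootstrap resamples, and report the winner's optimism-corrected AUC and how often each marker, and each window, ranks first;
- call any winner exploratory until it has been tested in a separate cohort.

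The cost is a few sentences in the analysis plan and a short bootstrap program; no new data are needed for the corrected report. The reported AUC will be lower, there may be no single winner, and the correction is partial (about 60% of the bias in the one setting tested), which is why the exploratory label is still needed.

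### Objective 2 asks which inflammation marker best predicts deterioration or death, but the plan studies only unspecified associations with death, which cannot rank the markers

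*Combined protocol and SAP*

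**What the plan says.** All references are to rows of the combined protocol and SAP.

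- **Objective(s).** The stem is "To evaluate changes in biomarkers associated with inflammation to determine". The second question under it is "which biomarker or indexes related to inflammation best predicted this deterioration or death".
- **Method.** The data to be extracted are "age, sex, blood pressure, oxygen saturation, survival status, CRP, and a CBC with differential from the time of admission, days 2-3 and 3-5". Three sampling windows are therefore stated, and day 3 falls in two of them.
- **Statistical analysis plan.** The outcome sentence is "Patient status (deceased or alive within 28 days after hospital admission) will be recorded". The only sentence linking markers to outcome is "Association between factors (age, creatinine, CRP, cortisol, genito-thyroid index) and death will be studied". The summaries named are descriptive: "Means and standard deviations, numbers, percentages and confidence intervals will be used to describe quantitative and qualitative variables, respectively".
- **Context of the study.** Two different cortisol quantities appear. One is introduced with "Another marker is serum cortisol". The other is the group's own model, in which "effective tissue-level activity of cortisol can be modeled using a complete blood count with differential". That row also says it is still unclear which inflammation markers correlate most strongly with mortality, and when in the hospital stay.

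**The concern.** The objective is comparative and predictive, while the analysis is neither. An association can be expressed as a difference in means, an odds ratio per unit, a correlation or a p-value. The first two depend on each marker's own units, and a p-value also depends on how many patients had that marker measured. None of these puts CRP, the genito-thyroid index and cortisol on one scale unless the plan says how.

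The ranking is central. The sponsor's own background treats the link between inflammation and mortality as established, and presents the choice of marker and its timing as the open question. If the rule for calling a marker best is settled after the results are seen, the winner depends partly on that choice and its performance will tend to look better than it is. One candidate index comes from the authors' own group, so a rule fixed in advance also protects the credibility of the result.

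The objective also covers deterioration, for which the plan has no variable. A conclusion on it would have nothing behind it.

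**Working it through.** **Step 1: objective against analysis.**

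| Objective 2 needs | What the plan gives |
|---|---|
| A measure on which markers can be ranked | Association, with no effect measure, model or test named |
| A comparison between markers | None |
| The window whose values are ranked | Three windows in Method; the SAP does not say which feeds the association |
| Outcome: deterioration or death | Vital status to 28 days; no definition or variable for deterioration |

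**Step 2: factors against data.** Age and CRP are on the Method list. The genito-thyroid index is the neutrophil-to-lymphocyte ratio and can be computed from the blood count with differential. Cortisol can be obtained from the listed data only as the blood-count-derived index. Creatinine appears once in the document, as an SAP factor, and has no route from the listed data. Setting age and creatinine aside leaves three inflammation candidates: CRP, cortisol and the genito-thyroid index.

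**Step 3: size.** The plan has no figure to reproduce. Assumptions: 20% deaths; n=150 (30 deaths, 120 survivors) or n=300 (60 and 240); AUC 0.65.

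Hanley-McNeil variance, with A the AUC, d deaths and s survivors:

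Var = [A(1−A) + (d−1)(A/(2−A) − A²) + (s−1)(2A²/(1+A) − A²)] / (d·s)

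At A=0.65 the three terms are 0.2275, 0.0590 and 0.0896.

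- n=150: (0.2275 + 29×0.0590 + 119×0.0896)/3600 = 0.00350; SE 0.0592; 95% half-width 1.96×0.0592 = 0.116.
- n=300: (0.2275 + 59×0.0590 + 239×0.0896)/14400 = 0.00174; SE 0.0418; half-width 0.082.

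**Step 4: effect of picking the best of three in one window.** Binormal simulation, 4,000 runs, between-marker correlation 0 / 0.5 / 0.8. Overstatement is the mean apparent AUC of the selected marker minus its true AUC.

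| True AUCs | Quantity | n=150 | n=300 |
|---|---|---|---|
| All 0.65 | Mean apparent best | 0.696 / 0.684 / 0.670 | 0.683 / 0.675 / 0.665 |
| All 0.65 | Overstatement | 0.046 / 0.034 / 0.020 | 0.033 / 0.025 / 0.015 |
| 0.60, 0.65, 0.70 | Overstatement | 0.032 / 0.016 / 0.005 | 0.016 / 0.007 / 0.002 |
| 0.60, 0.65, 0.70 | Wrong marker ranked first | 29% / 20% / 9% | 20% / 11% / 3% |

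Repeat runs agreed to within about 0.003 on the AUC scale.

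**The case against.** The strongest reply is that this is a short retrospective plan, and that associations, suitably scaled, would let a reader order the markers. That stands only in part. They could give an informal order, but the plan does not commit to a scale, and the choice would be made with the data in view.

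Several stronger readings are tempting and are not supported:

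- **That no sampling windows are given.** Method states three. What is missing is which one enters the ranking.
- **That creatinine will not be collected.** The data lists are loose. The SAP says eligibility criteria will be recorded, yet several of them, such as dementia and cirrhosis, are not on the Method list. The SAP's sentence on continuous data omits CRP, which Method includes. Naming creatinine as a factor may imply obtaining it. It is also not among the inflammation markers discussed in the background, so it barely touches Objective 2.
- **That cortisol data are missing.** The background points to the blood-count-derived index, reported there as better than serum cortisol at predicting mortality after myocardial infarction. The plan needs a label.
- **That a single winner will be chosen across all markers and windows, or by a standardised mean difference.** No text plans either, so larger overstatements computed on those premises do not belong here.
- **That Objective 2 requires added value over clinical variables.** It does not; that is good practice and optional.
- **That the results had been seen when the text was written.** The timetable ends in October 2020 and the references include 2021 publications, so part of the text is later than the timetable. This does not show what had been analysed.

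It is also fair that, when the markers truly differ, the selection overstatement (0.002 to 0.032) is well inside the confidence interval of any one AUC.

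**Conclusion.** The gap between Objective 2 and the planned analysis is real and should be corrected. Followed exactly as written, the plan yields associations with death that do not rank the markers on a common scale, and it can say nothing about deterioration. This rests on the text alone and needs no assumption.

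The numerical harm is uncertain and probably modest. It depends on assumed values for sample size, death rate, AUCs and correlations, none of which the documents give. The figures serve mainly to show that, at plausible sizes, the uncertainty around each AUC is wide enough for a marker to be named best by chance. Creatinine and cortisol are small reconciliations and would not justify the point by themselves.

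**What to change.** 1. For 28-day death, report each inflammation marker's AUC with a 95% CI in each window. Compare markers within a window by paired AUC differences in the same patients. Give patients and deaths per window, and assign day 3 to one window. State whether the level or the change from admission is ranked, since the objective speaks of changes.
2. If a best marker is named, report a bootstrap optimism-corrected AUC that repeats the within-window selection. Treat comparisons across windows as descriptive, because the patients contributing to each may differ.
3. Limit the Objective 2 conclusion to 28-day death unless deterioration is defined and extracted. Label the analysis post hoc if results have been seen.
4. Add creatinine to the extraction list or drop it from the factors. Label cortisol as the blood-count-derived index, or extract serum cortisol if that is meant.

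Optional: added value over age, sex, oxygen saturation and blood pressure.

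**Cost.** SAP wording and a few hours of programming. Keeping creatinine means one laboratory value per patient per time point: 150×3 = 450 at n=150, or 300×3 = 900 at n=300. Serum cortisol would add as many again. The statistical price is wider stated uncertainty and possibly no clear winner. Under the same assumptions, a paired test of AUC 0.70 against 0.65 was significant in at most about 27% of simulated studies at n=150 and 50% at n=300.

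### Does creatinine's absence from the listed data items leave one of the five planned factor analyses without data?

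*Combined protocol and SAP*

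**What the plan says.** The document is a single table covering protocol and analysis plan. Three of its rows bear on this point.

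- **Statistical analysis plan, factors.** "Association between factors (age, creatinine, CRP, cortisol, genito-thyroid index) and death will be studied". This is the only place in the document where creatinine appears.
- **Method.** The coded data to be entered from the records are "age, sex, blood pressure, oxygen saturation, survival status, CRP, and a CBC with differential", from admission and two later windows within the first five days.
- **Statistical analysis plan, data.** The row opens with a general reference to demographic and biological data. It then says "Categorical data will be collected for inclusion/exclusion criteria, gender, and patient living status", and gives the complete blood count as the continuous data.

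The Study population row contains one renal item, "Chronic renal failure on dialysis". Medical records are the only data source ticked, and the design is single-centre and retrospective.

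**The concern.** An analysis variable should be traceable to a data item. Here one of the five factors to be related to death has no entry in either list of data. The dialysis criterion is a yes/no status and cannot stand in for a measured creatinine. The Method does name CRP, the other chemistry test among the factors, so the omission cannot be put down to a habit of leaving chemistry out.

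The analysis is assigned to a separate organisation, which makes the written list more important than it would be for a single team. If the extraction had followed the Method row literally, the dataset passed on would hold no creatinine and that association could not be estimated. A reader of the results would then not know whether creatinine was dropped because it was never collected or because of what it showed.

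**Working it through.** No sample size, event count, significance level or effect size is stated, and the point depends on none of them. The check is a comparison of lists.

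**Step 1. Count the listed items.** The Method row names 7. The analysis plan's data sentences name 28-day status, eligibility criteria, gender, living status and the blood count. Gender is sex, both status items are survival status, and the blood count is already listed, so they add 1 new item (eligibility criteria). Total: 7 + 1 = 8 items, of which 0 is or yields a creatinine value.

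**Step 2. Trace each factor to a source.**

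| Factor | Source in the lists |
|---|---|
| Age | Listed in the Method |
| CRP | Listed in the Method |
| Genito-thyroid index | Derivable: the Context says the neutrophil-to-lymphocyte ratio is "referred to as the genito-thyroid index(GTi", and the differential count supplies it |
| Cortisol | Derivable if the modelled index is meant: the Context says that "effective tissue-level activity of cortisol can be modeled using a complete blood count with differential". Not listed if serum cortisol is meant |
| Creatinine | None |

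So 1 of 5 factors certainly lacks a listed source, and 2 of 5 on the serum reading of cortisol. The Context discusses both forms of cortisol and the plan does not choose between them.

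**Step 3. Ask whether the lists are meant to be complete.** The Method names five continuous items: age, blood pressure, oxygen saturation, CRP and the blood count. The plan's sentence on continuous data names one of these, so it omits 5 − 1 = 4, including two of the five factors (age and CRP). In the other direction, the Method omits the eligibility criteria that the plan says will be collected. Neither list is complete. If absence from a list meant that a variable was not collected, age and CRP would fail against the plan's own data sentence, which is plainly not intended. The rows have to be read together, and the factor list is itself one of the places where a study variable is named.

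**Step 4. Ask what depends on creatinine.** The second objective asks "which biomarker or indexes related to inflammation best predicted this deterioration or death". The Context names CRP, the neutrophil-to-lymphocyte ratio and cortisol as inflammation markers, and does not name creatinine. In the factor list creatinine stands with age as a general prognostic variable. Removing it leaves the association with death for each of the other factors as planned, because no joint model containing creatinine is specified.

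**Step 5. Check the timing.** The Timetable gives "Data collection of patients hospitalized between March and May 2020 : from June to July 2020". Four of the 17 references (numbers 2, 6, 11 and 17) are dated 2021, so this text is later than that window. If extraction ran on schedule, which is not stated, the dataset existed before this text and the Method row could not have misdirected it.

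**The case for a change.** The strongest case for a change is that relating factors to death is the only inferential analysis the plan names besides calculating the score, and one of its five inputs has no stated field or time point. A value being available in the chart does not put it in the dataset, and the Method states what is to be entered. The correction would also be cheap: one added item or one deleted word.

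The textual part of this stands. Creatinine is in no data list, and no redaction or extraction fault explains it. What does not follow is that the analysis is unsupported. A plan that names a variable for analysis and draws on existing records has told its analysts to obtain it. The missing time point is not special to creatinine, since the factor sentence gives none for CRP, cortisol or the index either. The Method's windows (admission, days 2-3, days 3-5) are the natural default, giving up to three values per patient. That the correction is cheap does not make it necessary, because neither version of it alters any other result.

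The ambiguity over cortisol is a fair remark and would raise the count from one to two. It is a question of definition, separate from the creatinine gap, and the Context offers a reading under which the listed data suffice.

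**Conclusion.** The lists disagree, but no change to the plan follows. The mismatch covers 1 of 5 factors, or 2 of 5 if serum cortisol is meant. It is an incomplete data list in a brief summary, of the kind analysts fill by extracting the variable that the factor list names. There is no effect on bias, on any error rate, on the other associations, or on the comparison of CRP, the genito-thyroid index and modelled cortisol under the second objective.

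This rests on two assumptions. The first is that creatinine can be retrieved from the records, which the retrospective record-based design makes reasonable but the documents do not confirm. The second is that the report states which factors were actually analysed. If creatinine was never extracted, the loss is one association with death, and a sentence in the report would cover it. The conclusion would be different if creatinine were an input to a specified joint model or a named primary marker, and the documents give no sign of either.

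### The planned marker–death associations give no role to the oxygen saturation, blood pressure and sex that the study extracts, so they cannot show whether a marker adds to bedside information

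*Combined protocol and SAP*

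**What the plan says.** The Method row lists what is taken from the records: "age, sex, blood pressure, oxygen saturation, survival status, CRP, and a CBC with differential from the time of admission, days 2-3 and 3-5". The Statistical analysis plan row adds that "Categorical data will be collected for inclusion/exclusion criteria, gender, and patient living status".

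That row then states one analysis against outcome: "Association between factors (age, creatinine, CRP, cortisol, genito-thyroid index) and death will be studied". The outcome is vital status at 28 days after admission. The row gives demographic and biologic data two uses, describing the population and computing the STC-19 score.

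The second objective is to find "which biomarker or indexes related to inflammation best predicted this deterioration or death". The public-interest row describes the intended use: "If this score is validated, it will provide care recommendations determined by the number of factors", with less demand on hospital, emergency and intensive care resources.

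Patients enter with "signs of severity (polypnea, saturation < 90% room air, dyspnea, systolic blood pressure < 90 mmHg, altered consciousness, somnolence, confusion) and/or co-morbidities", so the cohort mixes patients who have severity signs with patients who qualify on co-morbidity alone.

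**The concern.** Staff deciding where a patient should go already have age, sex, saturation and blood pressure. A blood marker earns a place in triage by what it adds to these. A patient who is hypoxaemic or hypotensive on arrival may be more likely to die and may also have more deranged inflammatory markers. If so, a marker can be associated with death without carrying any information of its own.

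An analysis that relates markers to death without bedside findings in the model cannot separate the two cases. The entry rule makes this relevant here, because bedside severity varies within the cohort. At stake is a marker or score being put forward for triage on an association that saturation and blood pressure would already have supplied.

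**Working it through.** **Step 1. Compare the two lists.**

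| Extracted (Method row) | Role against death (Statistical analysis plan row) |
|---|---|
| Age | Listed as a factor |
| CRP | Listed as a factor |
| CBC with differential | Enters through the genito-thyroid index, which the Context row equates with the neutrophil-to-lymphocyte ratio |
| Sex | None |
| Blood pressure | None |
| Oxygen saturation | None |
| Survival status | The outcome |

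Of the six items other than the outcome, three are used and three are not. In the other direction, creatinine and cortisol are to be related to death but are not in the Method list. Cortisol may mean the activity modelled from the CBC; the text does not say.

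**Step 2. Look for a model elsewhere.** No row names a regression model, an adjustment set, a clinical-only comparator or a measure of added value. Age stands beside the markers as a factor, and nothing says that they are adjusted for it.

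**Step 3. Illustrate the mechanism.** The plan gives no sample size, death count, mortality or effect size, so there is no figure to reproduce and every input below is an assumption.

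- Bedside severity S is standard normal, with logit P(death) = a + βS.
- The marker is M = ρS + √(1 − ρ²)·E, where E is independent noise. M has no effect of its own.
- Approximate crude log odds ratio per SD of M: ρβ / √(1 + k²β²(1 − ρ²)), with k = 16√3/(15π) ≈ 0.588 and k² ≈ 0.346.

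Three settings by hand:

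- β = ln 2 = 0.693, ρ = 0.3: 0.208 / √(1 + 0.346 × 0.480 × 0.91) = 0.208 / 1.073 = 0.194, odds ratio 1.21.
- β = ln 3 = 1.099, ρ = 0.5: 0.549 / √(1 + 0.346 × 1.207 × 0.75) = 0.549 / 1.146 = 0.479, odds ratio 1.61.
- β = 1.3, ρ = 0.7: 0.910 / √(1 + 0.346 × 1.690 × 0.51) = 0.910 / 1.139 = 0.799, odds ratio 2.22.

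Simulation with 400,000 patients per setting and ρ from 0.3 to 0.7 agrees:

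| Assumed mortality | Assumed β | AUC of S | Crude AUC of M | Crude OR of M per SD | OR of M with S in the model |
|---|---|---|---|---|---|
| 10–30% | ln 2 to ln 3 | 0.68–0.77 | 0.55–0.69 | 1.21–2.05 | 0.99–1.01 |
| 20% | 1.0 to 1.3 | 0.74–0.80 | 0.57–0.71 | 1.31–2.23 | about 1.0 |

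In the first grid, the AUC of S and M together equals that of S alone: the gain is 0.00. Also in that grid, the chance that the empty marker reaches two-sided p < 0.05 in a crude test is 9% to 79% at an assumed 100 patients and 14% to 98% at an assumed 200.

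The adjusted odds ratio of 1.0 holds by construction, because M was given no effect and S is measured without error. The useful result is the crude column: an ordinary-looking association can arise with nothing behind it.

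**The case against.** **Silence is not a specified crude analysis.** The plan says only that association will be studied. It never says unadjusted, univariable or limited to these five, and a joint model of all five factors, age included, would fit the words. This stands. A reader might infer a closed list analysed one factor at a time, and the documents do not establish that. But even a joint model of the five would leave out saturation, blood pressure and sex, and if the list is open, the adjustment set is simply unstated.

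**Objective 2 is a ranking of markers.** Comparing each marker's own discrimination is a legitimate answer to it. This stands too, and the crude comparison should stay. Added value is a further question, raised by the triage use. That use is worded conditionally and concerns the STC-19 score.

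**Saturation may lie on the pathway from inflammation to death.** The Context row treats inflammation as the common mechanism, so adjustment could absorb real marker signal. That would matter for a causal claim. For prediction at the door, a signal already visible in the saturation is not new information. It is one more reason to report both analyses.

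**Two further inferences are not supported.** One is that cardiac history is a specific confounder, because the indexes were developed in cardiac patients. The heart failure and infarction sentence concerns modelled cortisol activity; for the neutrophil-to-lymphocyte ratio, the Context row cites COVID-19 mortality evidence, and nothing shows that either index tracks cardiac history here. The other is that STC-19 will be compared unevenly with single markers. The plan describes no such comparison, and the score's formula is proprietary.

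**Sex is not a severity sign.** Correct: the argument rests mainly on saturation, blood pressure and age.

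**Conclusion.** The point holds in a limited form. Three extracted variables have no stated role in relation to death, and no adjusted or added-value analysis is specified. The listed analysis is sound as description and can rank markers by their own association with death. It cannot support a claim that a marker improves triage.

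The size in this study is unknown. The crude odds ratio of about 1.2 to 2.2 per SD for an uninformative marker rests on assumed mortality of 10–30%, assumed severity effects and assumed marker–severity correlations of 0.3–0.7. It does not show that any listed marker is uninformative, or that a ranking from this study would be wrong. The change is worth making before analysis because the bedside data are already being collected.

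**What to change.** 1. Keep the crude associations and each marker's own AUC as the direct marker comparison.
2. Prespecify a base logistic model for 28-day death on admission age, sex, oxygen saturation and systolic pressure. State that the saturation and pressure are admission values, since the Method row leaves unclear which items its time points cover.
3. Add to the base model, one at a time, admission CRP, genito-thyroid index, STC-19, and cortisol and creatinine where available. For each, report the adjusted odds ratio per SD, the likelihood-ratio test and the change in AUC with 95% CI.
4. Rest any claim of triage usefulness on step 3.
5. Note whether each saturation was on room air or oxygen, where the record says so. The entry criterion is a room-air value, and a reading on oxygen is not comparable with it.

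Cost: SAP wording, a few extra models and one optional data item, which retrospective charts may not always supply. The base model uses about four degrees of freedom. If deaths are few, use penalised estimation (Firth, with its penalised likelihood-ratio test, or ridge), or carry the base model as a single linear predictor. This covers admission markers and death only. The deterioration part of objective 2 and the later sampling windows need their own specification.
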